9.6 DATA MANAGEMENT

Patients' data will be gathered in Remote Data Capture (RDC) system.

The data management procedures to ensure the quality of the data will be described in detail in the Statistical and Epidemiological Analysis Plan (SEAP) available in TMF.

9.7 DATA ANALYSIS

9.7.1 Main analysis

All collected data will be analysed separately for patients starting with 40mg and \leq 30mg. Although due to anticipated low sample size in patients starting with \leq 30mg, it will be mainly for exploratory purpose. Baseline demographics will be analysed with descriptive statistics (N, median, mean, 25%, 75% percentile, SD) and compared descriptively between patients who have dose modifications within the first 6 months of Gi(l)otrif[®] treatment and those who do not. All the demographics, safety and efficacy data from this study in real-world setting will be compared with data from LUX-Lung 3 trial in descriptive manner.

Analysis of Safety:

[figure not shown]
Safety analysis will include all patients treated with Gi(l)otrif[®] and be descriptive in nature. Incidence and severity of ADRs according to Common Terminology Criteria for Adverse Events (CTCAE) criteria (version 4.0) ([R15-5988](#)) when available will be summarized and displayed in number/percentage. For patients who had Gi(l)otrif[®] dose modifications within the first 6 months of Gi(l)otrif[®] treatment, frequency and severity of the common ADRs pre- and post-dose modification will be analysed (\geq 40mg vs $<$ 40mg; and \geq 30mg vs $<$ 30mg). Missing or incomplete ADR dates will be imputed according to BI internal SOPs.

Analysis of Effectiveness:

Effectiveness analysis will include all patients treated with Gi(l)otrif[®]. Time on treatment is from the date of first dose of Gi(l)otrif[®] treatment to the date of last dose of Gi(l)otrif[®] treatment. Time to progression is from the date of first dose of Gi(l)otrif[®] treatment to the earliest date of documented progression (clinical, radiographic or both clinical/radiographic progression) or death. Time on treatment and time to progression will be estimated using Kaplan-Meier method, and the median along with two-sided 95% CI will be displayed (use the Greenwood's formula for estimation of standard errors). Log-rank test will be applied to compare between patients with and without dose modifications. Time on treatment and time to progression will be compared between patients who dose reduced to $<$ 40 mg within the first 6 months of Gi(l)otrif[®] treatment and those who remained on Gi(l)otrif[®] 40 mg once daily. This is in analogy to the analysis made on LUX-Lung 3 where a cut-off of 6 months was used as most dose reductions occur during this time.

In the analyses of the two time-to-event endpoints, missing or incomplete data are managed by standard survival analysis techniques. For patients still on treatment, time on treatment will be censored at the date of data collection. For patients still on treatment and without progression, time to progression will be censored at the date of data collection. For patients stopped treatment and without progression/death or progression/death date missing, time to

progression will be censored on the last contact date.

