Afatinib 40 mg/day (oral) is approved for the treatment of patients with advanced EGFRm+ NSCLC. Dose adjustments are recommended based on pre-defined tolerability criteria. A post-hoc analyses of the effects of afatinib dose reduction on adverse events (AEs), pharmacokinetics (PK) and PFS in the phase III LUX-Lung 3 trial showed that dose reductions occurred in 53% (122/229) of patients; the majority (86%) within the first 6 months of treatment. In patients who dose reduced, decreases in the incidences of drug-related all grade (grade \geq 3) AEs were 99.2% (20.5%) to 46.7% (4.1%) for diarrhea, 88.5% (26.2%) to 38.5% (3.3%) for rash/acne, 77.0% (12.3%) to 27.9% (0%) for stomatitis, and 44.3% (16.4%) to 36.9% (4.9%) for nail effects. Dose reductions tended to be more common in female patients, older patients, patients of Eastern Asian ethnicity, and patients with lower body weight. Dose reduction was more likely in patients with higher plasma concentrations of afatinib. On Day 43, patients who dose reduced to 30 mg \geq 4 days previously (n=38) had geometric mean plasma afatinib concentrations of 24.4 ng/mL, vs 23.7 ng/mL in patients who remained on the 40 mg dose (n=126). Median PFS was 11.3 months in patients who dose reduced during the first 6 months of treatment, vs 11.0 months in patients who did not (HR=1.25 [95% CI, 0.91–1.72]). [ASCO 2015, Yang et al, # 8073] ([P15-05676](#)).

Post-hoc analyses from LUX-Lung 3 suggest that tolerability-guided dose adjustment of afatinib is an effective measure to reduce treatment-related AEs without affecting therapeutic efficacy:

- The frequency and severity of treatment-related AEs was lower following dose reduction
- Tolerability-guided dose modification reduced the inter-patient variability of afatinib exposure, while maintaining efficacious plasma levels
- Efficacy outcomes were similar in patients who dose reduced due to AEs versus those who did not

This real-world data (RWD) study will help to understand if dose modifications are done similar as in LUX-Lung 3 trial and if the outcome on safety and effectiveness are as in trial settings.

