8. RESEARCH QUESTION AND OBJECTIVES

Research objective:

Data from real-world will help to understand if dose modifications are done similar as in LUX-Lung 3 trial and if the outcome on safety and effectiveness are as in trial settings. Furthermore, data on modified starting doses, the underlying reasons and effects on safety and outcome are needed.

Primary objective:

To assess the effects of Gi(1)otrif[®] dose modification on the frequency and severity of adverse drug reactions (ADRs), time on treatment and time to progression with Gi(1)otrif[®] in real-world setting and compare with data from LUX-Lung 3 trial in a descriptive manner.

Secondary objective:

To obtain information on frequency and reasons for a modified starting dose of Gi(1)otrif[®] in real-world setting.

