9.2 SETTING

The NIS will be conducted in about 25-30 sites globally which are experienced in lung cancer treatment. An average of 8-10 patients per site (with a maximum of up to 15 patients per site) is expected.

Patient participation in this NIS is voluntary. Patients were treated and are treated according to the standard of care independent of patient's consent to participate in this NIS.

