9.2.1 Selection of study population

Site selection:

Sites in countries with launch dates prior to 1st Jan 2015 and known to prescribe Gi(l)otrif[®] on a regular basis will be chosen. Asian and Non-Asian countries will be included.

Inclusion criteria:

All consecutive patients will be included if all the following criteria are present:

- Age \geq 18 years

Protocol for non-interventional studies based on existing data

BI Study Number 1200.270

c09038525-01

Proprietary confidential information © 2016 Boehringer Ingelheim International GmbH or one or more of its affiliated companies

- Patients with EGFR mutation (common mutations), TKI-naïve advanced NSCLC, treated with Gi(l)otrif[®] as the first-line treatment for NSCLC within the approved label
- Signed and dated written informed consent per regulations. (Exemption of a written informed consent for retrospective observational studies in some countries per local regulations and legal requirements.)

Exclusion criteria:

Patient won't be included if any of the following criteria is present:

- Any contraindication to Gi(l)otrif[®] as specified in label.
- Patients with uncommon mutations are excluded as uncommon mutations are not within label in all participating countries (e.g. USA).
- Patients still on treatment with Gi(l)otrif[®] will be excluded unless treatment period is ≥ 6 months.
- Patients treated with Gi(l)otrif[®] within an interventional trial.

A log of all patients included into the study will be maintained in the ISF at the investigational site.

Patients treated with Gi(l)otrif[®] in interventional trials are excluded to ensure the non-interventional setting of this study. The threshold of ≥ 6 months treatment with Gi(l)otrif[®] for patients being still on treatment was chosen to avoid early censoring and enable collection of mature data on ADRs and treatment duration. However, patients who stopped Gi(l)otrif[®] < 6 months will be included to avoid bias. All patients fulfilling inclusion and exclusion criteria from a site will be entered to avoid bias. The maximum of 15 patients per site was chosen to avoid bias by high proportion of patients coming from one site.

BI reserves the right to discontinue the study overall or at a particular study site at any time for the following reasons:

1. Failure to meet expected enrolment goals overall or at a particular study site.

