9.9 LIMITATIONS OF THE RESEARCH METHODS

The generalization and consequently the external validity of the study results, may be limited by the participation in the study of only sites that prescribe Gi(l)otrif[®] on a regular basis to ensure sufficient patient recruitment. Patients treated by investigators with less experience might experience more side effects during their treatment with Gi(l)otrif[®].

Methodological efforts have been taken to minimize selection bias: these efforts include the recommendation to include consecutive patients meeting each of the inclusion criteria and none of the exclusion criteria. In addition, this possible selection bias may be limited by the retrospective aspect of the data collection, data that have been already collected at the time of the study. Linked to this aspect is then the limitation due to data availability. Indeed, no additional data will be collected for the study purpose. So if the data is not available in the patient files, then this will be considered as missing data.

In addition, to reduce error in data collection, a standard study eCRF will be used, ensuring a measure of consistency among the collectors.

Another limitation is coming from the diverse handling of data collection from deceased patients which is allowed without informed consent in some countries but not in all.

However, no country-based analyses will be done. Given the median overall survival (31.6 months in LUX-Lung 3) and that time from launch of Gi(l)otrif to data collection in the participating countries is shorter than the median overall survival (OS) the majority of the patients are expected to be alive.

External validity is provided by the global approach of this study and the broad inclusion criteria but limited to patients treated within the label and at the selected, experienced sites. Internal validity will be given by source data verification.

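### The comparison with LUX-Lung 3 is crude: a case-mix difference would be visible in the demographics, but not how much of a gap from the 53% dose-reduction rate it explains

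*Protocol*

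**What the plan says.** The research objective in Protocol section 8 reads: "Data from real-world will help to understand if dose modifications are done similar as in LUX-Lung 3 trial". It also asks whether safety and effectiveness outcomes are as in the trial. The primary objective includes a descriptive comparison with LUX-Lung 3.

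The benchmark is in Protocol section 7: "dose reductions occurred in 53% (122/229) of patients". The same section says who was reduced: "Dose reductions tended to be more common in female patients, older patients, patients of Eastern Asian ethnicity, and patients with lower body weight".

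The comparison itself is in section 9.7.1: "All the demographics, safety and efficacy data from this study in real-world setting will be compared with data from LUX-Lung 3 trial", and the sentence ends by calling this comparison descriptive. That section also analyses patients separately by starting dose, and compares baseline demographics between those with and without a dose modification in the first six months.

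On the mix of patients, section 9.2.1 says "Asian and Non-Asian countries will be included" and gives no target share. The title page lists 13 countries, including Japan, Korea, Singapore and Taiwan. The only numerical limit is per site: "with a maximum of up to 15 patients per site".

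On adjustment:
- Section 9.3.3 marks covariates as not applicable.
- In Annex 2, checklist item 10.4 answers No to stratified analyses.
- Checklist item 10.5 answers Yes to methods for confounding adjustment and cites page 19.
- Section 9.9 states "However, no country-based analyses will be done".
- The SAP text available covers derived variables and date imputation only.

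**The concern.** If dose reduction is more frequent in some kinds of patient, the overall rate in a cohort depends on who is enrolled as well as on how physicians dose. Here the enrolled mix follows from which sites are chosen and how many patients each supplies. A real-world rate above or below 53% could then reflect a different proportion of East Asian, older, female or lighter patients, with the same dosing behaviour within each group.

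The planned side-by-side demographics would alert a reader to such a difference. They would not say whether it explains one point of the gap or all of it, and that is what a reader needs in order to judge whether practice is similar. Sections 9.9 and 9.12 discuss site experience, selection, data availability and consent. They do not mention case mix relative to LUX-Lung 3.

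**Working it through.** **Benchmark.** 122/229 = 0.533, which reproduces the stated 53%. There is no power calculation to reproduce: section 9.5 rests the size of 200 on similarity to the 229 patients of the LUX-Lung 3 analysis, and the abstract on feasibility.

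**Patients starting on 40 mg.** Section 9.5 expects 25-30% to start on a lower dose: 200 × 0.25 = 50 and 200 × 0.30 = 60. That leaves 140-150 starting on 40 mg; I use 145.

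**Shift from case mix alone.** With identical practice within each ethnic group,

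shift in crude rate = (difference in East Asian share) × (difference in reduction rate between the groups).

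The documents give neither term, so both are assumptions:
- low end: 0.20 × 0.15 = 0.03, or 3 points;
- high end: 0.40 × 0.30 = 0.12, or 12 points.

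Sex, age and weight could add to this or offset it.

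**Sampling noise.** The benchmark is itself an estimate from 229 patients, so the right yardstick is the standard error of the difference, with p = 0.533 and p(1 − p) = 0.2489:

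SE = √[p(1 − p)(1/n + 1/229)]

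| n | SE (points) | 95% half-width, 1.96 × SE | 3-point shift in SEs | 12-point shift in SEs |
|---|---|---|---|---|
| 145 | 5.3 | 10.4 | 0.6 | 2.3 |
| 200 | 4.8 | 9.5 | 0.6 | 2.5 |

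**What standardising would do (illustration).** Assume a LUX-Lung 3 East Asian share of 70%, a share of 40% here, a 20-point gap between groups and identical practice. To give 53.3% overall, the group rates must be 59.3% and 39.3%.
- Crude rate here: 0.40 × 59.3 + 0.60 × 39.3 = 47.3%, a gap of −6.0 points.
- Standardised to the 70/30 mix: 0.70 × 59.3 + 0.30 × 39.3 = 53.3%, a gap of 0.
- Precision at n = 150 (60 East Asian, 90 other): 1.96 × √[0.70² × 0.593 × 0.407/60 + 0.30² × 0.393 × 0.607/90] = 9.2 points, against 8.0 for the crude rate.

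**How far adjustment can go.** Four factors at two levels each give 2⁴ = 16 cells, and 145/16 is about 9 patients per cell before any missing chart data.

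**The case against.** The study is descriptive by design. Checklist item 2.1.4 marks formal hypotheses as not applicable, and there is no test against LUX-Lung 3 and no threshold for similarity. Dose-reduction frequency is not a listed primary or secondary outcome, and the comparison sentence in 9.7.1 names demographics, safety and efficacy. The practice question comes from sections 7 and 8. The plan sets demographics beside the trial, splits by starting dose and caps each site. All of this stands. It lowers the weight of the point but does not remove it, because stratified and standardised rates are also descriptive, and none of these steps shows how much of a gap case mix explains.

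Several stronger readings are tempting, and the documents do not support them:
- A reader might infer that the four factors cause dose reduction. Section 7 reports only a tendency.
- A reader might infer that any departure from 53% will be presented as physicians dosing differently. No section says so.
- A reader might extend the four factors to ADR frequencies. Section 7 ties them to dose reduction only.
- A reader might take the sentence on country-based analyses as ruling out analysis by ethnicity. It follows a remark on consent for deceased patients and does not mention ethnicity.

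Nor can it be said that no further analysis exists. The contents list has a blacked-out entry between 9.7.1 and 9.8, and the SAP refers to planned tables that are not shown. The No at item 10.4 argues against stratification there, though weakly, since 9.7.1 does split by starting dose.

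**Conclusion.** The point holds as a worthwhile, inexpensive improvement. The visible plan poses a question about similarity to LUX-Lung 3, reports that the benchmark varies with patient mix, leaves the mix open, and compares crudely. A case-mix difference would be seen but not quantified.

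The 3-12 point shift rests wholly on assumed shares and assumed rate differences. Comparing it with this study's sampling error alone (4.1 points at n = 145) could suggest a shift of about three standard errors. That treats 122/229 as exact. With the trial's own error included, the extreme is 2.3-2.5 standard errors, and much of the range falls inside the 95% half-width of 9.5-10.4 points. It would therefore be too strong to conclude that the comparison is invalid or that the external question cannot be answered. What can be said is that the planned figures would not show whether case mix matters.

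**What to change.** In Protocol section 9.7.1 and the SAP, for patients starting on 40 mg:

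- Show dose-reduction frequency, at any time and within six months, and the common ADRs, separately for East Asian and other patients, beside the same strata of the LUX-Lung 3 afatinib arm, with 95% CIs. Match the time windows: section 7 gives 53% overall with 86% of reductions in the first six months, so the six-month benchmark is about 0.86 × 53.3 = 45.8%.
- Add one overall reduction rate standardised to the LUX-Lung 3 ethnic mix.
- Treat sex, age and body weight one factor at a time, or through a single weighting model, and not by joint four-way cells.
- State that similarity will be judged from these figures together with the crude ones.

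In section 9.9, name case mix as a limitation, along with the remaining differences between a trial and a chart review that standardising cannot remove. Correct checklist item 10.5: the contents list places 9.7.1 on the cited page 19, and its visible text describes no confounding adjustment.

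The cost is a short text change and a few tables. Section 9.3 already collects sex, date of birth, ethnicity and weight, and the abbreviations list identifies LUX-Lung 3 as the sponsor's own trial. Intervals widen in the smaller strata. If 145 patients split evenly (an assumption), the half-width for a rate near 53% is 1.96 × √(0.2489/72.5) = 11.5 points per stratum, against 1.96 × √(0.2489/145) = 8.1 for all 145.

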7. RATIONALE AND BACKGROUND

The first marketing approval of afatinib was granted on 12 Jul 2013 in the USA (trade name Gilotrif[®]) for the indication of first-line treatment of patients with metastatic non-small cell lung cancer (NSCLC) whose tumors have epidermal growth factor receptor (EGFR) exon 19 deletions or exon 21 (L858R) substitution mutations as detected by an FDA-approved test. It was approved in the European Union on 25 Sep 2013 (trade name Giotrif[®]) as monotherapy indicated for the treatment of EGFR TKI-naïve adult patients with locally advanced or metastatic NSCLC with activating EGFR mutation(s). [REDACTED]

The approval of Giotrif[®] was based on the results observed in the pivotal trial LUX-Lung 3 study. The LUX-Lung 3 study investigated the efficacy of chemotherapy compared with afatinib, a selective, orally bioavailable ErbB family blocker that irreversibly blocks signaling from epidermal growth factor receptor (EGFR/ErbB1), human epidermal growth factor receptor 2 (HER2/ErbB2), and ErbB4 and has wide-spectrum preclinical activity against EGFR mutations. A total of 1,269 patients were screened, and 345 were randomly assigned to treatment (afatinib or chemotherapy). Median progression-free survival (PFS) was 11.1 months for afatinib and 6.9 months for chemotherapy (hazard ratio [HR], 0.58; 95% CI, 0.43 to 0.78; P=.001). Median PFS among those with exon 19 deletions and L858R EGFR mutations (n=308) was 13.6 months for afatinib and 6.9 months for chemotherapy (HR, 0.47; 95% CI, 0.34 to 0.65; P=.001). The most common treatment related adverse events were diarrhea, rash/acne, and stomatitis for afatinib and nausea, fatigue, and decreased appetite for chemotherapy. Patients reported outcomes (PROs) favored afatinib, with better control of cough, dyspnea, and pain ([P13-07382](#)).

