9.5 STUDY SIZE

The post-hoc analysis of LUX-Lung 3 providing the rationale for this study was based on 229 patients with 53% patients experiencing dose reduction. With a sample size of 200 we would be in the same range as in the LUX-Lung 3 analysis which provided robust data. It will be sufficient to analyse the effects of dose modification on patients' safety and effectiveness and to compare it with data from LUX-Lung 3 trial descriptively.

Based on feedback from physicians we expect 25-30% patients starting with a lower dose.

There will be around 50 patients starting with a modified dose, and around half of them with further de-/escalation. This is a sufficient sample size to get some impression on the reasons of a modified starting dose in real-world setting.

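### The LUX-Lung 3 comparator is not restricted to common EGFR mutations, although this study enrols only patients with common mutations

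*Protocol*

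**What the plan says.** The primary objective (Protocol section 8) includes a descriptive comparison with LUX-Lung 3. Section 9.7.1 carries it out broadly: "All the demographics, safety and efficacy data from this study in real-world setting will be compared with data from LUX-Lung 3 trial". No mutation subset of that trial is named.

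Section 9.2.1 restricts enrolment here: "Patients with uncommon mutations are excluded as uncommon mutations are not within label in all participating countries". The reason given is labelling. The effect on the comparison is not discussed.

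Section 7 reports two LUX-Lung 3 results. For all randomised patients: "Median progression-free survival (PFS) was 11.1 months for afatinib and 6.9 months for chemotherapy". For the subset that matches this study: "Median PFS among those with exon 19 deletions and L858R EGFR mutations (n=308) was 13.6 months for afatinib".

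Section 9.5 identifies the reference analysis: "The post-hoc analysis of LUX-Lung 3 providing the rationale for this study was based on 229 patients". Section 9.7.1 takes its 6-month split for time on treatment and time to progression from that analysis. Section 7 gives its median PFS as 11.3 months in patients who reduced in the first 6 months and 11.0 months in those who did not.

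The mutation difference is not mentioned in section 9.9 (limitations), section 9.12 (bias) or the derived-variable text of the SAP (section 1).

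**The concern.** The study asks whether effectiveness in routine care resembles that in the trial. No test, margin or adjustment is planned against LUX-Lung 3, so readers will set one median beside another. If the trial median comes from a population that includes uncommon mutations and the real-world median does not, part of any difference reflects who was enrolled. The protocol's own figures show that the choice of LUX-Lung 3 population moves the reference by 2.5 months. Left open, that choice could also be made after the results are known.

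**Working it through.** **Inputs (all Protocol)**
- LUX-Lung 3 afatinib median PFS: 11.1 months overall, 13.6 months in Del19/L858R (section 7).
- LUX-Lung 3 size: 345 randomised, of whom 308 had Del19/L858R, both arms together (section 7).
- Post-hoc analysis: "dose reductions occurred in 53% (122/229) of patients"; medians 11.3 and 11.0 months by reduction in the first 6 months (section 7).

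**Reproducing the stated rate.** 122/229 = 53.3%, which agrees with the stated 53%.

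**Which population are the 229?** The two dose-reduction groups together make up the 229. Where two groups make up a cohort, the pooled survival curve lies between the two group curves. The pooled median therefore falls between, or with censoring very near, the group medians of 11.0 and 11.3. The all-mutation 11.1 lies in that interval; 13.6 lies well outside it. So the 229 are, by inference, essentially the all-mutation afatinib population.

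**Size of the mismatch**
- Against the overall median: 13.6 − 11.1 = 2.5 months; 2.5/11.1 = 22.5%.
- Against the two post-hoc medians: 13.6 − 11.3 = 2.3 months (2.3/11.3 = 20%) and 13.6 − 11.0 = 2.6 months (2.6/11.0 = 24%).
- In reverse, a real-world median of 11.1 falls short of the matched figure by 2.5/13.6 = 18%.

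**Share of patients involved.** (345 − 308)/345 = 37/345 = 10.7%, both arms pooled. The documents do not give the share in the afatinib arm. If 10.7% holds there, 229 × 308/345 ≈ 204 of the 229 had common mutations.

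**Can case mix alone produce 2.5 months?** Assume exponential survival with a common-mutation median of 13.6 and a common share of 308/345 = 0.893. The pooled median t solves

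0.893 × 0.5^(t/13.6) + 0.107 × 0.5^(t/m) = 0.5,

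where m is the uncommon-mutation median (assumed, since the documents give none).

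| Assumed m | Pooled median | Gap to 13.6 |
|---|---|---|
| 5 months | 12.2 | 1.4 |
| 3 months | 11.7 | 1.9 |
| 0 (all progress at once) | 13.6 × log2(2 × 0.893) = 11.4 | 2.2 |

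Under this model the pooled median cannot fall below about 11.4, so a 10.7% share does not yield the whole gap. The remainder would have to come from curve shape, sampling error or a larger uncommon share in the afatinib arm. The documents give no confidence interval for either median.

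**Is the gap visible at this study's size?** Assume exponential survival and 120 to 160 progression events (the documents give no event count). A cohort with median 13.6 then has a 95% interval of 13.6 × exp(±1.96/√d): 11.4 to 16.3 months with d = 120, and 11.6 to 15.9 with d = 160. Both lie above 11.1. This treats 11.1 as fixed and ignores its own error, so it illustrates scale only.

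**The case against.** The strongest reply is that the protocol nowhere names an all-mutation benchmark. Section 9.7.1 leaves the LUX-Lung 3 subset unspecified, section 7 prints 13.6 next to 11.1, and the post-hoc analysis is cited for the 6-month cut-off and for study size. Some analysis text is also not visible: a heading after 9.7.1 is blacked out in the table of contents, and the available SAP text covers derived variables only. This stands to the extent that the benchmark population is inferred and a restriction may exist in text that cannot be seen. It does not remove the point, because section 9.7.1 as it reads sets no restriction and the analysis it copies fits only the all-mutation figure.

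Second, the comparison is descriptive, and the only planned test is the within-study log-rank comparison, in which every patient has a common mutation. That is correct; the test is untouched. Nor do the documents show that mutation mix alters the contrast between reduced and non-reduced patients within LUX-Lung 3 (HR 1.25). What shifts is the absolute medians.

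A reader might infer three stronger things that the documents do not support:
- **A net bias in favour of the real-world result.** Other features act in the opposite or an unknown direction. Section 9.2.1 excludes patients still on treatment for less than 6 months but keeps those who stopped early, which tends to shorten the estimated times. Section 9.5 expects 25-30% to start on a lower dose. Section 9.7.1 counts clinical progression.
- **That the whole 2.5 months is case mix.** The exponential check above argues against that.
- **That the ADR and dose-reduction comparisons are distorted too.** Section 7 relates dose reduction to sex, age, ethnicity, body weight and plasma concentration, and no document links mutation type to tolerability.

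**Conclusion.** The point holds for time to progression and, less directly, for time on treatment. As section 9.7.1 reads, a common-mutation cohort would be compared with a LUX-Lung 3 reference that is not limited to common mutations. On this factor alone, a cohort equal to the matched LUX-Lung 3 patients could look up to about 2.5 months (22.5%) better than the trial, and a median of 11.1 months could pass as equivalent while being about 18% below the matched figure.

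The conclusion rests on the inference that the 229 patients are the all-mutation afatinib population, and on taking both published medians at face value. The 2.5 months is an upper figure for the mutation effect; the net direction of all differences between the two studies is not established. No sample size, error rate or within-study test changes. This should be corrected before analysis, because the comparison belongs to the primary objective and the better comparator is within the sponsor's reach.

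**What to change.** State in section 9.7.1 and in the SAP that the primary LUX-Lung 3 comparator for time to progression and time on treatment is the afatinib-treated Del19/L858R subset, re-derived from the sponsor's own trial data (1200.32), and that the 6-month dose-reduction split is recomputed in that subset. The matched version of the 11.3 versus 11.0 split cannot be derived from the documents, so the sponsor has to produce it. Show the published all-mutation figures alongside for reference. In section 9.9, list the mutation mismatch as a limitation of any comparison that still uses all-mutation data. Re-deriving the ADR and dose-reduction tables in the same subset is optional, for consistency only.

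The cost is a small amount of re-tabulation and a smaller comparator: about 204 instead of 229 patients, roughly 10% fewer, if the 37/345 share holds in the afatinib arm.

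Separately, whether death counts as an event needs to be settled before any comparison with PFS: section 9.7.1 includes it in time to progression and the SAP derivation does not.
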